Aim 1: Use rtfMRI-NF and motor imagery to train CA participants to improve motor accuracy.

- Aim 1.1: Train CA participants (N=30) to engage neural regions during motor imagery that are associated with overt finger tapping at slow (1 Hz) and fast (4 Hz) speeds.
- *Aim 1.2:* Correlate motor imagery skill (i.e., slider bar distance from target) with overt tapping performance.

• *Aim 1.3:* Evaluate the relations between overt tapping accuracy and neurological symptoms as well as motor imagery skill with offline assessments of motor imagery ability.

Aim 1 will use rtfMRI-NF during motor imagery to train CA participants to improve motor accuracy. Thirty CA participants will receive NF during motor imagery in an experiment in which we hypothesize that 1) CA participants will be able to control a NF interface; 2) imagery skill will be positively correlated to improvements in overt tapping accuracy; and 3) overt tapping accuracy will correlate with neurological signs, whereas motor imagery skill will correlate with assessed motor imagery ability.

Aim 2: Translate rtfMRI-NF learning into at-home therapy strategies for continued training.

- Aim 2.1: Examine whether motor imagery strategies from rtfMRI-NF training translate into successful at-home therapy training
- *Aim 2.2:* Compare motor imagery performance during rtfMRI NF with at-home motor imagery benefits.

Aim 2 will translate rtfMRI-NF learning into at-home therapy strategies for three weeks of continued training in which we hypothesize that 1) continued practice with imagery strategies will lead to additional improvements in motor timing and precision, and 2) performance during rtfMRI-NF training will positively correlate with at-home motor imagery performance.

Exploratory

Aim 3: Design next-generation approaches to rtfMRI-NF. The data from Aim 1 will be analyzed to optimize the future rtfMRI experiments in the CA population. We will examine whether the NF session can be streamlined to deliver more accurate NF in shorter sessions. To enable future studies to operate within an experimental medicine frame work we will examine three major questions. Aim 3.1 Are there group differences in CA versus healthy controls? Aim 3.2 Are healthy models of motor imagery viable for CA participant NF? Aim 3.3 Can the NF session be streamlined to deliver more accurate NF in more efficient sessions?

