Figure 1. Finger tapping speed and accuracy in CA. Top row: The CA group showed impaired accuracy at 1, 2 (trend), 3, and 4 Hz. Bottom row: The CA group tapped too fast at 1 Hz and too slow at 4 Hz. Yellow= group means. Error bars denote standard error [1].

slider bar that moved to the left as participants tapped too slow and to the right as they tapped too fast. We anticipated that CA participants would be able to use the external cues of the slider bar to correct tapping errors in real time, rather than rely on internal models of timing intervals.

Tapping accuracy, measured by root-mean-squared error (RSME) relative to target, was impaired at all tapping rates. Relative to controls, the CA group's tapping speed was too slow at 4 Hz, and too fast at 1 Hz. Tapping too fast at 1 Hz suggest an inability to control movements to slow down. Over/undershoot corrections in finger movements likely averaged out and masked group differences in speed 2 and 3 Hz, but were revealed in the slow (1 Hz) and fast (4 Hz) conditions. In CA, higher symptom severity, as measured by the International Cooperative Rating Scale (ICARS), was associated with slower tapping and greater error magnitude. Together, these results suggested that accuracy and speed are dissociable measures, with accuracy being the more sensitive measure of motor impairment in CA. Moreover, the 1 and 4 Hz conditions represented especially interesting tapping rates to study given the contrasting behaviors at each speed. We conducted a follow-up study to explore whether the feedback from the slider bar improved or degraded tapping behavior. We found that both groups slowed their tapping speed in the absence of continuous feedback, but the CA group's tapping accuracy deficits persisted. Based on the differences between 1 and 4 Hz, we speculate that 4 Hz may be close to the tapping limits of CA participants, but 1 Hz represents a trainable target for improving motor timing from paced visual feedback. Thus, this application's focus on 1 and 4 Hz builds on a foundation of preliminary data and aims to tease apart deficits in production from those of top-down feedback processing. We conducted an fMRI pilot study to identify neural activity patterns associated with right-

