Exclusion criteria: History of Axis I psychiatric disorders (including alcohol and drug dependence), severe or unstable medical disorder, non-ataxia related neurological disorders, such as stroke or epilepsy, history of head injury that resulted in a loss of consciousness greater than 5 minutes and/or neurological sequelae, any condition that is contraindicated for the MRI environment (e.g., metal in the body, pacemaker, claustrophobia), or currently pregnant, and clinical diagnosis of multiple system atrophy (MSA, due to the disruption of the central autonomic network) or Friedrich's ataxia (FA, due to extensive involvement of the spinal cord and loss of sensory fibers in the peripheral nerves). MSA and FA differ substantially from other forms of CA and would greatly complicate interpretation of the data. Eligible subjects may be asked to refrain from medications that affect the central nervous system that would also make data difficult to interpret (e.g., sedatives) for an appropriate period of time prior to scanning. Participants will be excluded if they do not have a home computer with internet available to complete the 3-week at-home component of the study protocol.

6. Drugs/ Substances/ Devices

- a. The rationale for choosing the drug and dose or for choosing the device to be used.
- N/A
- b. Justification and safety information if FDA approved drugs will be administered for non-FDA approved indications or if doses or routes of administration or participant populations are changed.
- N/A
- c. Justification and safety information if non-FDA approved drugs without an IND will be administered.

N/A

7. Study Statistics

a. Primary outcome variable.

1) Overt tapping accuracy improvements will be analyzed by comparing the mean accuracy on overt tapping between baseline and final measures (pre- and post- NF) to compute a delta

measure that will indicate magnitude of accuracy improvement at each frequency (1 and 4 Hz). This will be analyzed using paired t-tests within frequency conditions.

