2) At-home overt tapping accuracy improvements will be analyzed by comparing the mean accuracy on overt tapping between baseline and final measures at home (pre- and post- 3-week at-home therapy training) to compute a delta measure that will indicate magnitude of accuracy improvement at each frequency (1 and 4 Hz). This will be analyzed using paired t-tests within frequency conditions. As a follow-up analysis of improvement during the 3-week therapy (for training Groups 2 and 3 who perform daily overt tapping exercises), the mean accuracy of overt tapping at both frequencies will be measured for each session and compared using repeated measures ANOVAs and post-hoc t-tests as appropriate.

b. Secondary outcome variables.

1) The relation between imagery accuracy and tapping accuracy with supplemental assessments of imagery and motor symptoms will be analyzed using non-parametric correlation tests, such as Spearman's rank-order correlation coefficient test, because of the ordinal values in the KVIQ and ICARS assessments. Mean imagery accuracy and tapping accuracy scores from the final MRI assessment will be compared separately to the KVIA an ICARS.

2) The relation between brain activity during imagery NF and overt tapping improvements will be analyzed using Pearson correlations between the mean of region of interest activity (minus rest) during NF training and the RSME delta scores.

3) The influence of ancillary measures on overt tapping and motor imagery accuracy will be analyzed using non-parametric correlation tests (e.g., Spearman's rank) because of the ordinal values in the HAM-A, HAM-D, CCAS, and WRAT assessments. Mean imagery accuracy and tapping accuracy scores from the final MRI assessment will be compared separately to each of the assessments.

c. Statistical plan including sample size justification and interim data analysis.

We plan to enroll 30 participants in this study. The sample size was determined through a power analyses using G*Power 3.1.9.2 software [40]. Because motor imagery, with or without rtfMRI-NF, has never been used as a treatment approach for people with cerebellar ataxia (CA), as proposed here, our power analyses are extrapolated from information we have obtained that in three prior studies that support the premise and feasibility of Aim 1, which is to use rtfMRI-NF and motor imagery to train CA participants to improve motor accuracy.

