In our first study, the behavioral RSME deficits exhibited by cerebellar ataxia participants while performing the same overt tapping task as proposed in Aim 1 was quite robust at both 1 Hz and 4 Hz conditions (relative to controls, N=17 per group) [1]. Applying these data to our model revealed that a **sample size of at least 12** participants per group yielded at least 82% power at the .05 level, one-tailed, to reject the null hypothesis of no differences between groups, based on an effect size of at least .79 (large). Although the proposed study will not include healthy

controls, at least 12 CA participants should be sufficient to elicit RSME performance impairments.

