In our second study, a functional MRI study of CA participants and healthy controls while performing the same overt tapping task as proposed in Aim 1 revealed several brain regions that differed between groups at the 1 Hz and 4 Hz conditions (N=6 controls, N=10 ataxia): notably, right M1 and right cerebellar lobe V. Contrast values (1 Hz tapping – rest) for these regions were computed, using atlas-based boundaries [41, 42] for CA participants and healthy controls separately and entered into analyses. For the M1 region of interest (ROI), a sample size of at least 13 participants per group yielded 82% power at the .05 level, two-tailed, to reject the null hypothesis of no difference between groups at the 1 Hz condition, based on an effect size of 1.2 (large). For cerebellar lobe V, a sample size of at least 9 participants per group yielded 83% power at the .05 level, two-tailed, to reject the null hypothesis of no difference between groups. Similarly, strong between-group differences were revealed at the 4 Hz condition for the M1 ROI. Atlas-based contrast values (4 Hz tapping – rest) for M1 were computed for each group and entered into analyses. A sample size of at least 8 participants per group yielded 84% power at the .05 level, two-tailed, to reject the null hypothesis of no difference between groups at the 4 Hz condition, based on an effect size of 1.6 (large). However, group differences for cerebellar lobe V, not were significant in our fMRI study at the 4 Hz condition because the CA group was able to recruit this region vigorously in this tapping condition. Given the low number of participants per group in the functional MRI pilot study, additional brain ROIs were identified by trending between-group differences and entered into the model: left premotor cortex and bilateral lobes VIIB. For these ROIs, a sample size of 19-29 participants per group yielded at least 80% power at the .05 level, two-tailed, to reject the null hypothesis of no group differences, based on an effect size of at least .78 (large). These measures are conservative given that the ROIs were atlas-based rather than task-based (i.e., the ROI boundaries included voxels that did not differ between groups). Thus, a sample size of 29 would be expected to reveal neural activation abnormalities in a number of regions within the cortex and cerebellum in CA participants.

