In our third study, rtfMRI-NF was applied to healthy adults (N=17) while performing the overt tapping and imagery tasks proposed in Aim 1. Results revealed that several brain regions engaged during motor imagery positively correlated with RSME improvements: bilateral M1, right premotor cortex and the SMA. Atlas-based contrast values (motor imagery – rest) for these ROIs were computed. Entering into the model the correlation value and standard deviations between the mean contrast values per ROI and mean RSME "delta" revealed that **a** sample size of 17 - 22 participants yielded at least 81% power at the .05 level, one-tailed, to reject the null hypothesis of no linear relationship between motor imagery activation and RSME improvements.

Taken together, we propose to enroll N=30 CA participants into this study. This N will be overpowered for some aspects of the study, such as tapping accuracy. However, we are also taking into consideration that the rtfMRI-NF data was based on healthy controls, and we anticipate greater variability in rtfMRI-NF training in the CA participants. Moreover, a sample size of 30 will allow us some room to make additional comparisons with the at-home therapy data (Aim 2) and exploratory MRI data analyses (Aim 3).

Sample size may be underpowered for the some of the proposed comparisons across aims. The amount of motor imagery necessary to improve overt tapping performance in CA patients is unknown. We modeled our power analysis parameters to target Aim 1. However, we will compare the neuroimaging data with at-home therapy performance variables (Aim 2) and will use the data from Aim 1 to conduct exploratory analyses to improve future protocols (Aim 3). The current sample size may be too small to detect significant results on all comparisons. Nevertheless, we consider the data we collect here to be highly informative for future studies and will serve as pilot data (and power analyses) for future grant applications.

Statistical methods that will be used with respect to each outcome measure:

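### Does Section 7a need a stated alpha, sidedness and one-frequency rule for its 1 Hz and 4 Hz paired t-tests?

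*Combined protocol and SAP*

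**What the plan says.** Section 7a lists two primary outcomes. Item 1 compares tapping accuracy before and after neurofeedback. Item 2 does the same for the home phase ("pre- and post- 3-week at-home therapy training"). Each defines a "measure that will indicate magnitude of accuracy improvement at each frequency (1 and 4 Hz). This will be analyzed using paired t-tests", and the sentence goes on to confine each test to one frequency. That gives four primary paired tests. Neither item states alpha, sidedness or how a result at one frequency alone is to be read. The general methods text at the end of Section 7c names types of test and adds none of these.

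The .05 level appears only in the Section 7c power calculations, which concern other tests:

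- The first study, a between-group comparison of tapping error, "yielded at least 82% power at the .05 level, one-tailed".
- The second study, between-group contrasts in brain regions, for example "yielded 82% power at the .05 level, two-tailed".
- The third study, a correlation with improvement in tapping error, gave "at least 81% power at the .05 level, one-tailed, to reject the null hypothesis of no linear relationship".

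On direction, an Aim 2 hypothesis in Section 2 is that "continued practice with imagery strategies will lead to additional improvements in motor timing and precision", with no frequency named. On the two frequencies, the Background says "we speculate that 4 Hz may be close to the tapping limits of CA participants, but 1 Hz represents a trainable target". On purpose, Section 7c says the data "will serve as pilot data (and power analyses) for future grant applications".

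**The concern.** Two things appear open until the data are seen. The first is sidedness. Both power calculations that involve tapping error are one-tailed, and tapping error is the measure behind the primary outcomes, so one-sided primary tests cannot be ruled out from the text. A result significant one-sided but not two-sided could then be reported either way.

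The second is the reading of a split result. The Background expects 1 Hz and 4 Hz to behave differently, so improvement at only one of them is foreseeable. If that were reported as success for the aim, each aim would have two chances of a false positive. Combined with one-sided testing, the nominal 5% could nearly double. What is at stake is which statements may be called primary results. The estimated changes and their confidence intervals are the same whichever convention is used.

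**Working it through.** **Inputs.** n = 30 (Section 7c), assumed complete. Two frequencies per outcome (Section 7a). Alpha of .05 per test is assumed, because every power calculation uses it. The correlation r between the 1 Hz and 4 Hz changes is not given, so a range is shown. Item 2 is taken as pooled over the three home groups. Section 7a does not say so, but it names particular groups only for its follow-up analysis.

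**The plan's own figure.** The plan states no error rate or power for the primary paired tests. The nearest figure is the first study's 82% (12 per group, effect size 0.79, one-tailed .05). As a two-group t-test this gives 59.1%; as a one-sample or paired test with n = 12 it gives 82.1%. That mismatch is a separate matter and does not enter the calculations below.

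**1. Reading each frequency separately.** Each test stands for its own claim. The false-improvement rate per claim is 2.5% with a two-sided .05 test and 5% with a one-sided .05 test. There is no inflation.

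**2. Supposing that either frequency counts.** With independent changes:

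- two-sided .05, improvement direction: 1 − 0.975² = 0.0494
- one-sided .05: 1 − 0.95² = 0.0975

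With correlated changes (bivariate normal):

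| r | two-sided .05 | one-sided .05 |
|---|---|---|
| 0 | 4.9% | 9.75% |
| 0.5 | 4.5% | 8.8% |
| 0.7 | 4.2% | 8.0% |
| 0.9 | 3.5% | 6.8% |
| towards 1 | 2.5% | 5% |

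A simulation of paired t-tests at n = 30 (400,000 runs per r) agrees: 4.9, 4.6, 4.2 and 3.6% two-sided, and 9.7, 8.8, 8.1 and 6.9% one-sided, for r = 0, 0.5, 0.7 and 0.9. Whatever r is, including negative values, the rate cannot exceed the sum of the two tail areas: 2 × 2.5% = 5% two-sided and 2 × 5% = 10% one-sided.

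So a rate above 5% for a claim of improvement needs both unstated choices at once: one-sided tests and an either-frequency claim.

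**3. Sidedness alone.** Critical t on 29 df is 1.699 one-sided and 2.045 two-sided. Divided by √30 = 5.477, these are observed standardised changes of 0.310 and 0.373. The chance that one test falls between them is 2.5% under no effect, 13% at a true standardised change of 0.3 and 8% at 0.53. At 0.53, power is 88% one-sided and 80% two-sided.

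**4. Split results.** If both true changes are 0.53, exactly one frequency is significant (two-sided) in 32%, 23%, 18% and 10% of trials for r = 0, 0.5, 0.7 and 0.9. This is ordinary loss of power, not a false claim. If only one frequency truly responds, a split occurs in about 78% of trials, and it is then nearly always the correct finding.

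**5. Would a formal correction help?** A Holm step across the two frequencies would raise the standardised change detectable at 80% power from 0.529 to 0.589 at its stricter step, where power at 0.53 falls from 80% to 70%. It would guard a claim that the plan does not make.

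**The case for a change.** The strongest case for a change is that the gap comes from the protocol's own text. A reader who assumes two-sided .05 meets two one-tailed calculations, both on tapping error. The Background anticipates different behaviour at the two frequencies, yet nothing says what improvement at one of them means. Calling the data a pilot is not a full answer, because they are to support later power analyses and grant applications, and the claim of improvement travels with them. Two sentences would close the gap without new data.

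Part of this stands. Sidedness is not stated, and the text cannot prove which was meant. Writing it down in advance would be tidier, and a result with t between 1.70 and 2.05 would be open to dispute.

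The rest does not carry the weight put on it:

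- The one-tailed calculations address a between-group deficit and a correlation, not the paired change, so they do not set the convention for Section 7a.
- Only Aim 2 has a numbered hypothesis of mean improvement. Aim 1's three hypotheses concern control of the feedback interface and correlations, which weakens any inference of one-sided testing there.
- The either-frequency rule is supplied by the concern. Section 7a points the other way, with a change score and a test for each frequency.
- The remedy, separate claims by frequency, is what the wording already implies.

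**Conclusion.** The concern does not call for a change. Section 7a leaves out alpha and sidedness, but this is a gap that an analyst fills sensibly: two-sided tests at .05, reported for each frequency with 95% confidence intervals. No stated rule leads to a wrong result, and writing the convention down would not give a better method.

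The inflated rate, 5% to 9.75% for r from 1 to 0, arises only if one-sided .05 tests are combined with an either-frequency claim, and the plan states neither. With two-sided tests the same claim carries 2.5% to 4.9%. A single claim across both aims would carry more (1 − 0.975⁴ = 9.6% two-sided and 1 − 0.95⁴ = 18.5% one-sided, if all four tests were independent), but the plan treats the aims as separate questions.

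These error rates assume .05 per test and two tests per outcome. The thresholds and power figures also assume 30 complete pairs and, for item 2, pooling of the home groups. If item 2 were tested within groups of 10, the critical t on 9 df divided by √10 would give thresholds of about 0.58 one-sided and 0.72 two-sided, and there would be six tests. The conclusion on sidedness and per-frequency reading would be unchanged. The consequence is small in any case: estimates and intervals are unaffected, Section 7c concedes that the sample may be too small for some comparisons, and it presents the data as a basis for later studies.

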In general, due to the novelty of the rtfMRI-NF methodology as applied to clinical populations, methods have varied across studies, and there is still much to learn about how to optimize procedures. Nevertheless, rtfMRI-NF holds great potential as a motor rehabilitation tool. The proposed project will pursue this line of research by using rtfMRI-NF and motor imagery to train CA participants to engage their motor network and improve motor function. We will also test the feasibility of translating this training into at-home therapy. We will use rtfMRI-NF data collected here to develop next-generation approaches to machine learning-based rtfMRI-NF that will inform future protocols.

4. Study Procedures

a. Study design, including the sequence and timing of study procedures (distinguish research procedures from those that are part of routine care).

To address the objectives listed above, we plan to sample patients with cerebellar ataxia. For participants with cerebellar ataxia, this will be comprised of: 1) a screening phone call, 2) medical record review, 3) one study visit conducted by one of [name] research staff, which will be comprised of both remote, in-person activities, and neuroimaging as detailed below.

The specific study procedures are as follows:

First, a screening phone call will be placed to assess eligibility for participants with cerebellar ataxia. The screening phone call will involve the use of screening scripts to identify if patients are eligible and willing to participate in the research. Furthermore, screening will check for two issues 1) clinical appropriateness and 2) MRI Safety. The only screening test that must be done in-person after consent is obtained is a pre-MRI pregnancy test. Patients with cerebellar ataxia

will also specifically be asked for permission to review their medical records prior to the study visit to confirm eligibility. We will examine patient records in EPIC for additional medical information that may contain relevant study variables.

Next, the first study visit will be coordinated and performed by one of [name] research staff. This will involve a) written informed consent, b) interviewer-administered clinical history questionnaires, c) participant-administered surveys, d) neuropsychological testing, and e) MRI imaging at the Kennedy Krieger Institute.

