When the neuropsychological testing portion of the visit is completed, they will then be trained on a cognitive task that will be administered inside the MRI. If they are a woman of childbearing age, they will be given a urine drug pregnancy test. If the pregnancy test is positive, they will be removed from the study and PHI and any data collected thus far will be destroyed. After training and pregnancy test if needed, they will be escorted to the F.M. Kirby Research Center across the street, which houses the MRI scanner. Participants will be asked to arrive 1 hour before the MRI scan is scheduled to begin. Total time spent in the scanner will be approximately < 1 hour, and

Task	Approximate Time (minutes)
Training on cognitive test (outside the scanner beforehand)	10
MPRAGE	6
Overt tapping	12
Motor imagery	12
Overt tapping	12

we will reserve 1 full hour to allow time to get in and out of the scanner for this movement disordered population.

Participants will perform an overt tapping test as a baseline measure of online task performance. Therapy begins the next day and lasts for 21 days (participants complete at least 5 days per week to accommodate scheduling conflicts). A final measure of overt tapping will be performed the day after therapy ends. Participants will be randomly assigned to one of three training conditions. Group 1, imagery only; Group 2, overt tapping only; and Group 3, imagery plus overt tapping. During imagery, participants will view the task while imagining that they are finger tapping in time with the flashing cursor, using the imagery strategies identified during their rtfMRI-NF session. During overt tapping, participants will finger tap in time with the flashing cue.

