Participants will be instructed to find a quiet room with minimal distractions and remain in a comfortable seated position with their hands resting on the keyboard. All tests include blocks of trials in which either 1 or 4 Hz cues are presented. In the baseline and final measures, a session will consist of one 4-minute test comprised of 12 blocks; each frequency will be presented six times. In the 3-week therapy component, a session will consist of two 2-minute tests comprised of six blocks each; each frequency will be presented three times per block. In all sessions, frequency blocks will be pseudorandomized such that the first block will always be the 1 Hz frequency, and the same frequency will be presented in no more than three consecutive blocks. All blocks begin with 5 seconds of rest, followed by 15 seconds of the flashing cue. After completion of their experience for the day (e.g, vividness of imagery, perceived tapping precision, etc.).

	BASELINE M	EASURE	3 WEEKS OF AT-HOME THERAPY CONDITIONS				FINAL MEASURE	
	Overt tapping (4 min)	Daily log (3 min)	Imagery (4 min)	Overt tapping (4 min)	Imagery + overt tapping (2 + 2 min)	Daily log (3 min)	Overt tapping (4 min)	Daily log (3 min)
Group 1 (n=10)	X	X	X			X	X	X
Group 2 (n=10)	X	X		X		X	X	X
Group 3 (n=10)	X	X			X	X	X	X

b. Study duration and number of study visits required of research participants.

Each participant will have 1 in-person study visit (day 1) that will take about 3-4 hours. Days 2-23 of the study will consist of at-home therapy 5x weekly that may take up to 10 minutes to complete. At-home therapy includes a baseline online measure and log (7 minutes), group designated tasks (See table below) and log (7 minutes), and a final online measure and log (7 minutes). The total duration of the study is 2 years of data collection and analyses (allowing up to 3 additional years of data analyses).

General Study Protocol					
Event	Tasks Completed	Duration			
Screening	Clinical appropriateness	15-20 minutes			
(phone)					
	Consent*, pre-MRI pregnancy test	25-30 minutes			
Screening					
(In-person)					
In-person	Task orientation	10-15 minutes			
visit	MRI: Anatomical scan and rtfMRI-NF	1 hour (42 min			
		active MRI)			
	Questionnaires*, assessments*, neurological exam, at-home	2 hours			
	instructions				
At-home	Baseline online measure & log	7 minutes			
therapy	Training according to group assignment: Group 1 = motor	7 minutes per			

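### Participants are randomised to three at-home training conditions, but the plan specifies no comparison between them; the primary at-home test is a paired t-test that does not mention group

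*Combined protocol and SAP*

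**What the plan says.** Section 4a sets up a randomised comparison: "Participants will be randomly assigned to one of three training conditions". The conditions are imagery only (Group 1), overt tapping only (Group 2) and imagery plus overt tapping (Group 3). The at-home therapy table gives 10 participants to each. A daily session is 4 minutes of imagery, 4 minutes of tapping, or 2 minutes of each.

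Aim 2 stands under the primary objectives in section 2. Aim 2.1 is worded openly: "Examine whether motor imagery strategies from rtfMRI-NF training translate into successful at-home therapy training". The first Aim 2 hypothesis goes further, stating that "continued practice with imagery strategies will lead to additional improvements in motor timing and precision". The Background describes this part of the study as feasibility: "We will also test the feasibility of translating this training into at-home therapy".

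Section 7a, item 2, makes at-home change a primary outcome: "At-home overt tapping accuracy improvements will be analyzed by comparing the mean accuracy on overt tapping between baseline and final measures at home". The test is a paired t-test at each of 1 and 4 Hz. The text does not say whether all 30 participants are pooled or each group is tested separately. A follow-up repeated-measures ANOVA across sessions covers Groups 2 and 3 and names no group term.

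**The concern.** Random assignment is the only design feature that can separate the type of at-home training from retest and time effects, and the stated analysis does not use it. The paired t-test is the only planned test of baseline-to-final at-home change.

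The outcome is overt tapping. Groups 2 and 3 practise that task daily for three weeks, and every group takes the test twice. Tapping practice or retest alone could therefore make the paired test significant. The plan does not say that such a result would be read as evidence for imagery. But hypothesis 1 of Aim 2 concerns imagery practice, and no other planned test of at-home change bears on it. If the group comparison is left unspecified, its outcome, model and contrasts can also be chosen after the data are seen.

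**Working it through.** **1. Search for a between-group comparison**

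| Place | What it covers | Compares the randomised groups? |
|---|---|---|
| 7a item 2, primary test | Paired t-test at each frequency | No mention of group |
| 7a item 2, follow-up | ANOVA over sessions, Groups 2 and 3 | No group term; Group 1 does no daily tapping, so has no data for it |
| 7b | Correlations | No |
| 7c, sample size | Neuroimaging against at-home performance; unspecified further at-home comparisons | No test or contrast named |
| 7c, statistical methods | Within-participant comparisons, correlations, non-parametric tests for ordinal scales | No |
| Aim 3.1 and the first two power calculations in 7c | Ataxia against healthy controls | Different groups |

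The power analysis was aimed at Aim 1, so there is no stated figure for the at-home comparison to reproduce.

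**2. How often the paired test is significant without any effect of imagery**

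The documents give no training effect, SD of the change or pre-post correlation. All gains below are assumptions, in units of the SD of the change within a group.

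For a common retest gain *g*, the paired t statistic is noncentral t with n − 1 df and noncentrality *g*√n. The entries are the probability of exceeding the upper two-sided 5% point, P(T > t(0.975, n − 1)).

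| Common gain *g* | Pooled, n = 30 | Within one group, n = 10 |
|---|---|---|
| 0.2 | 18% | 8% |
| 0.3 | 36% | 13% |
| 0.5 | 75% | 29% |

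Now suppose that imagery-only does not change and both tapping groups gain equally. Simulation of the pooled test (100,000 replicates) gives 40% at group means (0, 0.5, 0.5) and 76% at (0, 0.8, 0.8).

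The in-scanner session contains two 12-minute overt tapping runs (section 4a), which could reduce later retest gains.

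**3. Precision of the randomised contrasts**

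ANCOVA with three groups of 10 and baseline as covariate has df = 30 − 4 = 26 and t(0.975, 26) = 2.056. In units of the outcome SD, with pre-post correlation *r*:

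SE = √(1 − r²) × √(2/10 + (x̄₁ − x̄₂)²/Sxx)

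Here x̄₁ and x̄₂ are the baseline means of the two groups and Sxx is the within-group baseline sum of squares. The second root averages 0.456 over 40,000 simulated baselines, which allows for chance imbalance.

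- r = 0.7: half-width 2.056 × 0.714 × 0.456 = 0.67 SD; 80% power at 0.95 SD; power at 0.5 SD 32%.
- r = 0.5: half-width 2.056 × 0.866 × 0.456 = 0.81 SD; 80% power at 1.15 SD; power at 0.5 SD 23%.

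Full simulation of the ANCOVA fit (20,000 replicates) agrees: rejection under no difference 5.2% and 5.1%, coverage 94.8% and 94.9%, power 80% at the differences above.

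The SD of the change is √(2(1 − r)) outcome SD, that is 0.775 at r = 0.7 and 1.000 at r = 0.5. In SD-of-change units the half-widths are therefore 0.86 and 0.81, and the differences with 80% power are 1.22 and 1.15.

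**4. Alternatives**

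- Group contrast on the deltas, df = 27: half-width 2.052 × √(2(1 − r)) × √0.2 = 0.71 SD (r = 0.7) and 0.92 SD (r = 0.5).
- Paired change within one group of 10: half-width t(0.975, 9)/√10 = 2.262/3.162 = 0.72 SD of the change.

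**The case against.** The strongest reply is that the plan makes no comparative claim. Aim 2.1 only examines whether strategies translate, and the additional improvement in hypothesis 1 may mean improvement beyond the scanner session, which is a baseline-to-final quantity. On that reading a paired test fits. This stands as far as it goes, and the paired change should stay as a description. It does not give the randomisation a use, and it does not help hypothesis 1, which attributes the improvement to imagery practice.

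Second, the text may intend a paired test within each group. Group 1 does no daily tapping, so its change would be free of tapping practice, and a common retest gain would reach significance less often (8%, 13% or 29% in the table). That is fair, but retest and time effects remain in Group 1, and separate within-group tests are still not a comparison between groups.

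Third, section 7c concedes that the sample may be too small for all comparisons and presents the data as a pilot for later studies. That excuses an imprecise comparison, not an unspecified one. Estimates by randomised group would serve the pilot purpose directly.

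Fourth, two contrasts at two frequencies raise multiplicity. If all four were tested with a Bonferroni adjustment, the half-widths would grow to about 0.87 and 1.06 outcome SD. The proposal is to report estimates with intervals, so an adjustment is not essential, but the plan should say which is intended.

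**Conclusion.** The concern holds and should be fixed. A primary outcome measured under a three-way randomisation has no analysis by allocation, and the one planned test of at-home change can be significant from tapping practice or retest alone. This reading of the text does not depend on any assumed number.

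The error rates are illustrative. Those for n = 30 apply only if the test pools all participants, and every gain and correlation is assumed. Part of the limit lies in the design: without an untrained arm, no analysis gives the effect of imagery against no training. The randomised contrasts would still show how the training types compare, though only large differences (about 0.95 to 1.15 outcome SD) would be detected with 80% power.

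**What to change.** Add to section 7a, item 2, for each frequency:

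> Final at-home accuracy will be modelled by ANCOVA on baseline at-home accuracy and training group (three levels). Group 1 v Group 2 and Group 3 v Group 2 will be reported as estimates with 95% confidence intervals, together with the paired change within each group.

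Also:

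- State whether the existing paired t-test pools all 30. Keep the overall change as a description of improvement with any training, and rest comparative statements about imagery on the randomised contrasts.
- State what the contrasts mean. Group 1 v Group 2 sets imagery against overt practice of the outcome task. Group 3 v Group 2 replaces half the tapping with imagery (2 + 2 v 4 minutes). Neither gives the effect of imagery against no training.
- State that the contrasts are pilot estimates without multiplicity adjustment, or name the adjustment.

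A group comparison of the deltas would also close the gap, with wider intervals (0.71 and 0.92 against 0.67 and 0.81 outcome SD).

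The cost is wording only, with no new data or visits. The downside is wide intervals and low power for moderate differences (23% to 32% at 0.5 SD), so the contrasts will not be a decisive test.
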